5.6.2 Evaluability for Gingivitis (GI) Outcomes

Subjects' gingivitis outcome data (e.g. Löe-Silness, Number of Bleeding Sites, Pocket Depth) will be assessed for evaluability based on the following criteria:

- 1) Visit and Product Criterion
For purposes of evaluability, a *missed visit* occurred when an eligible subject (still pregnant) did not attend a visit.
 - a) Visit Criterion: All monthly GI data for subjects who *missed* 2 or 3 eligible post-baseline monthly visits will be non-evaluable.
 - b) Product Supply Criterion: (for those who missed 0 or 1 post-baseline visit): If product supply was not received (via shipment or in person) at the previous monthly visit, then the current monthly GI visit will be non-evaluable.
- 2) Examiner Error: Subjects who had their baseline examination performed by examiner #129 will have all of their monthly GI data (BL, M1, M2, M3) declared non-evaluable.
- 3) Failed Entrance Criteria: Subjects who had any of the following at Baseline will have all of their monthly GI data declared as non-evaluable
 - Autoimmune disease
 - Type 2 Diabetes
 - > 24 weeks GA
 - < 30 bleeding sites
- 4) Protocol Deviation: Subject's monthly GI data where any of the following occurred will be declared non-evaluable
 - Multiple GI examinations at a single scheduled visit (2 examinations on 1 day) or same examinations repeated on 2 separate days
 - GI examination performed prior to examiner calibration
- 5) Failed Continuance Criteria: Subject's monthly GI data where there is evidence of the following will be non-evaluable
 - Insufficient product availability to assure test product compliance (from general comments or Continuance Criteria)
 - Evidence/documentation of consistent non-compliance with assigned test product use (either from general comments or continuance criteria)
- 6) Intervening dental procedures that might affect GI assessment will be non-evaluable
- 7) Oral topical antibiotics within 1-2 weeks of monthly GI visit (Peridex, essential oils, triclosan, chlorhexidine) will have that GI visit data declared non-evaluable.

6.0. Statistical Methods and Determination of Sample Size

All statistical tests will be 2-sided tests except where noted; and any treatment difference p-values less than 0.05 will be cited as statistically significant. The analysis for the evaluable population will be considered as the primary population and the Intent-to-Treat (ITT) analyses will be considered secondary.

The primary test will be the treatment effect test for 3-month change from baseline for Löe-Silness. No adjustments for multiple testing will be employed.

All statistical tests will be carried out using SAS® version 9 (SAS Institute Inc., Cary, NC).

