# 17. Hypotheses

Primary Hypothesis:

**Null Hypothesis**: There is no difference between treatment groups with respect to the mean Löe-Silness change from baseline score at each visit when an adjustment is made for the baseline Löe-Silness score.

Alternative Hypothesis: There is a difference between treatment groups with respect to the mean Löe-Silness change from baseline score at each visit when an adjustment is made for the baseline Löe-Silness score.

Secondary Hypothesis:

**Null Hypothesis:** There is no difference between treatment groups with respect to the mean gestational age when an adjustment is made for baseline demographic variables (e.g. smoking, evidence of preterm birth, etc.)

**Alternative Hypothesis**: There is a difference between treatment groups with respect to the mean gestational age when an adjustment is made for baseline demographic variables (e.g. smoking, evidence of preterm birth, etc.)

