The monthly gingivitis endpoints were the primary outcome measure, with the Month 3 evaluation being the primary time point of interest. Maternity outcome data (gestational age, birth weight, etc.) were abstracted separately from medical records as secondary variables with gestational age being of most importance. An interim analysis of the primary and secondary outcomes was performed by an independent statistician, and the target population size was adjusted. An independent Data and Safety Monitoring Board has assessed study design, conduct and outcomes at prescribed intervals with respect to study integrity, subjects' safety and evaluability.

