6.4 Birth Outcome Endpoints

Null Hypothesis: There is no difference between treatment groups with respect to the mean birth outcome when an adjustment is made for baseline demographic variables (e.g. smoking, evidence of preterm birth, etc.)

Alternative Hypothesis: There is a difference between treatment groups with respect to the mean birth outcome when an adjustment is made for baseline demographic variables (e.g. smoking, evidence of preterm birth, etc.)

Statistical analyses to determine treatment differences for mean Gestational Age and mean Birth weight will be analyzed using an analysis of variance (ANOVA) model with demographic factors such as previous pre-term birth (< 37 weeks; Y/N), self-reported smoking during pregnancy (Y/N), mother's weight at delivery (in grams), Study site and treatment. Interactions of these demographic variables with treatment will also be investigated for inclusion into the model. If the interactions are not significant at the 10% level then they will be eliminated from the final model. 95% confidence intervals will also be generated on the treatment difference of the mean gestational age and mean birth weight.

If any of the data does not satisfy the normality criterion, then transformations will be considered to improve normality or analogous nonparametric methods will be employed.

In addition, gestational age will be categorized as preterm (gestational age < 37 weeks) or term (gestational age \geq 37 weeks) for subsequent analyses and tested for treatment differences using logistic regression with the same demographic factors as described above. Gestational age will also be analyzed for treatment differences as a time-to-event variable using the log-rank test (and Kaplan Meier curves) and Cox Regression (adjusting for demographics/covariates). Other categorizations may also be used to identify early preterm births: 20 to < 34 weeks (early preterm), 34 to <37 weeks (late preterm), \geq 37 weeks; or low birth weight (< 2500 grams).

The distribution of birth weight will also be generated within the following gestational age categories (< 34, 34 to <35, 35 to <36, 36 to <37, 37 to <38, 38 to <39, \geq 39 weeks) for each treatment group using box plots.

Additional subgroups may be defined for analyzing birth outcome data, such as the following:

- By Study Site
- By Race (Caucasian, Black, Other)
- By Gestational Age at enrollment (8 to \leq 12 weeks, >12 to \leq 16 weeks, >16 to \leq 20 weeks, >20 to \leq 24 weeks)

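### SAP 6.0 allows any maternity p-value below 0.05 to be called significant, and no rule says which of the several maternity tests decides

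*SAP*

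**What the plan says.** SAP 6.0 settles the primary analysis clearly: "The primary test will be the treatment effect test for 3-month change from baseline for Löe-Silness". The evaluable population is primary and ITT is secondary. On significance it says "All statistical tests will be 2-sided tests except where noted", then "any treatment difference p-values less than 0.05 will be cited as statistically significant", and finally "No adjustments for multiple testing will be employed".

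For birth outcomes, SAP 2 lists the maternity data "as secondary variables with gestational age being of most importance". The Protocol's only secondary hypothesis (section 17) concerns one quantity: "There is no difference between treatment groups with respect to the mean gestational age", after adjustment. Protocol 15 calls birth weight ancillary.

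SAP 6.4 is wider. Its hypotheses refer to the mean birth outcome in general. It says "treatment differences for mean Gestational Age and mean Birth weight will be analyzed using an analysis of variance (ANOVA) model". The preterm/term split is to be "tested for treatment differences using logistic regression with the same demographic factors as described above", and gestational age is also analysed by log-rank test and Cox regression. Early and late preterm categories, low birth weight and a list of subgroups are optional.

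No section of either document sets a testing sequence, a gate, an alpha split or a family-wise error rate for these analyses.

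**The concern.** Leaving secondary endpoints unadjusted behind one primary test is acceptable when their p-values are reported as nominal. SAP 6.0 instead commits the sponsor to calling each treatment difference below 0.05 significant.

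The maternity outcomes are also more than background. They form part of the objective (Protocol 2). The starting sample size came from gestational-age variability (Protocol 11). The interim re-estimation used gestational age and birth weight, and 150 subjects were added (SAP 3).

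As written, a statement that the regimen improves birth outcomes could rest on whichever maternity test crosses 0.05, even if mean gestational age, the one quantity with a formal hypothesis in the Protocol, shows nothing.

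**Working it through.** **1. The plan's own figures.** Inputs from SAP 6.8: n = 300 per group, two-sided α = 0.05. Approximate power is Φ(δ / (σ√(2/n)) − 1.96).

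- Gestational age, δ = 1.1 weeks, σ = 4.1: 1.1 / (4.1 × 0.08165) = 3.286, and Φ(1.326) = 0.908. The plan says 90%.
- Löe-Silness, δ = 0.05, σ = 0.185: 0.05 / (0.185 × 0.08165) = 3.310, and Φ(1.350) = 0.912. The plan says at least 90%.

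Both reproduce. The documents give no family-wise error rate to reproduce.

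**2. Bounds that need no distribution.** For k tests each at 5% under the null, the chance of at least one rejection lies between 5% (all tests always reject together) and k × 5%. With independent tests it is 1 − 0.95^k: 9.75% for k = 2, 14.3% for k = 3, 18.5% for k = 4. The maternity tests are correlated, so the answer lies below the independent figure for the same k.

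**3. Null simulation.** There were 8,000 runs in each of three scenarios, with 300 per group. A random 87% were evaluable, matching the interim ratio 163/188 = 0.867 in SAP 3. Everything else is assumed:

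- Gestational age: 75-85% of births from N(39.2, 1.3) weeks. The rest are 38 weeks minus an exponential with mean 4, limited to 16-41 weeks. About 14-23% are preterm.
- Birth weight: 3350 g plus 120 or 170 g per week from 39.2, plus normal error with SD 480 or 400 g. Its correlation with gestational age is about 0.5-0.8.
- Tests: unadjusted two-group comparisons. Cox was left out because it nearly duplicates the log-rank test.

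Each evaluable-population test on its own rejected in 4.5-5.6% of runs.

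| Maternity tests counted | At least one p < 0.05 |
|---|---|
| Mean gestational age, mean birth weight | 7.5-8.9% |
| plus preterm birth | 10.5-11.8% |
| plus log-rank (four core tests) | 13.4-14.8% |
| plus early preterm and low birth weight (optional) | 18-20% |
| Four core tests in evaluable and ITT populations | 17-19% |
| Four core tests plus gestational age in 13 subgroups (optional) | 41-43% |

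The first four rows are cumulative and use the evaluable population; the subgroup row does too. The simulated gestational-age SD was about 2.7-3.3 weeks, below the planning value of 4.1. Scale does not affect null error, but the shape of the tail affects how strongly the tests move together, so these are ranges and not estimates for this trial.

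**4. Options for control.**

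- One named maternity test at 0.05: gestational-age power stays at 0.908.
- Bonferroni at 0.025 on gestational age and birth weight: Φ(3.286 − 2.241) = Φ(1.045), about 0.85.
- Gestational age tested only after a significant Löe-Silness result: 0.912 × 0.908 = 0.83 if the tests are independent.

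**The case against.** The best defence is that the plan already has a hierarchy: one primary variable, time point, test and population. Maternity data are secondary, gestational age is ranked first among them, and the Protocol's only secondary hypothesis is mean gestational age. SAP 6.4 places the preterm split among its subsequent analyses. The absence of adjustment is disclosed. Any inflation figure depends on which tests one chooses to count.

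Most of this stands. Naming the primary keeps its error at 5%, and gestational age does have an order of importance. No single percentage can be attributed to the plan. What does not stand is the inference that ranking is enough. SAP 2 ranks importance but does not say which test decides, and the significance rule in SAP 6.0 applies to every treatment difference whatever its rank.

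Stronger readings are tempting, and the documents do not support them:

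- *The gingivitis conclusion is inflated.* It is not, because it rests on one pre-specified test.
- *The trial has a 15% false-claim rate.* That figure needs assumed distributions and a particular choice of four tests.
- *The rate is 20% or 40%.* Those totals count categories and subgroups that SAP 6.4 only permits. A rank test should not be added either, since nonparametric methods there are a fallback for non-normal data.
- *Gestational age must be gated on Löe-Silness.* A gate would hold the pair of claims at 5% when neither effect exists, against 1 − 0.95² = 9.75% ungated if independent. It would also reduce power on the endpoint that set the sample size. That is a choice for the sponsor.

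**Conclusion.** The concern holds for the maternity claims only. Every treatment-difference p-value below 0.05 may be called significant, several maternity tests are planned, and none is designated as decisive. The chance of at least one false significant maternity result is about 8-9% for the two means and about 13-15% for the four core tests. It is about 17-19% if those four are counted in both populations and 18-20% if early preterm and low birth weight are added in one.

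These sizes rest on assumed null distributions and on the tests counted. The direction does not: the rate exceeds 5% unless all the tests always reject together.

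**What to change.** Add to SAP 6.0, before the blind is broken (SAP 5.5 already requires the SAP to be complete by then), wording to this effect:

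> The treatment effect on mean gestational age (Section 6.4 ANOVA, evaluable population) is the single key secondary test, at two-sided 0.05. Birth weight, preterm categories, log-rank, Cox, subgroup and ITT maternity results are reported with confidence intervals and nominal p-values and are not described as statistically significant.

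Limit the existing general significance sentence so that it does not override this. Section 6.4 should also fix the deciding model in advance. Its factor list is open-ended, interactions are kept or dropped at the 10% level, and transformation or nonparametric methods are possible, so the 5% level is secure only once those choices are settled.

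The cost is SAP wording. No analysis is dropped, the primary test is untouched, and gestational-age power stays at about 0.91 on the plan's assumptions at 300 per group. The real concession is that birth weight or preterm birth could not be claimed as significant on its own. If the sponsor wants birth weight to support a claim too, splitting alpha at 0.025 each lowers gestational-age power to about 0.85. Gating gestational age on Löe-Silness is optional and lowers it to about 0.83 if the tests are independent.

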6.1 Subject Disposition

The number and percent of subjects who were enrolled, randomized, randomized and then dropped (reasons for drops), and completed will be summarized.

6.2 Demographic and Baseline Characteristics Summaries

Demographic variables will be summarized across all evaluable subjects {Pregnancy Outcome and Gingivitis Outcome (Month 3) populations} and ITT subjects by: 1) treatment group and 2) treatment group within site. For variables that are categorical in nature (race, marital status, insurance, etc.), the number and percentage of subjects in each category will be presented by site and treatment group. For variables that are continuous in nature (age, baseline bleeding, etc.), the mean, standard deviation, minimum and maximum values will be presented for each treatment, site and overall.

The Medical History data collected at Baseline will be summarized by treatment group and the Obstetrical History will be summarized and tested by treatment to assess balancing across groups.

Comparisons between treatment groups will be performed for categorical variables with Pearson's Chi-square, Fisher's Exact test or Cochran-Mantel Haenszel test (for ordinal responses) as appropriate, and comparisons of continuous variables will be assessed using a two-sample t-test or Wilcoxon Rank Sum test.

These comparisons will be done to assess to degree to which the randomization procedure balanced the treatment groups with respect to the variables of interest.

6.3 Gingivitis Endpoints

Null Hypothesis: There is no difference between treatment groups with respect to the mean gingivitis change from baseline when an adjustment is made for the respective baseline gingivitis score and other demographic parameters.

Alternative Hypothesis: There is a difference between treatment groups with respect to the mean gingivitis score change from baseline when an adjustment is made for the respective baseline gingivitis score and other demographic parameters.

Statistical analyses for gingivitis efficacy endpoint will be based on whole-mouth average Löe-Silness change from baseline scores (Baseline score minus post treatment score) and will be considered the primary variable, with Month 3 the primary time point of interest. An analysis of covariance (ANCOVA) will be performed to determine treatment differences on the whole mouth average gingivitis reduction scores with the baseline gingivitis score as the covariate and also including study site, treatment, and the interaction of site and treatment as factors in the model. The interaction of treatment with the covariate will also be assessed for significance. If the interactions are not significant at the 10% level then they will be eliminated from the final model.

Additionally, 95% confidence intervals will be generated on the treatment difference for the average change from baseline scores. Separate analyses will be performed for each visit. The within-treatment difference from baseline gingivitis score will also be tested versus zero for each visit using the adjusted means from the ANCOVA model

The same analyses will also be generated for the reduction of Total Number of Bleeding sites and Pocket Depth reduction from baseline at each visit.

Testing for normality of the gingivitis endpoints will be carried out using Shapiro-Wilk test and residual plots. For non-normal data, a transformation such as taking the natural log (e.g., Total Number of Bleeding Sites) will be implemented or a non-parametric analysis will be carried out.

In addition to the ITT and Evaluable populations, the GI analysis will be carried out on the Intent-to-Treat subjects without examiner #129 data.

Additional subgroups may be defined for analysis on the gingivitis data, such as the following:

- By Study Site
- Subjects who had the same examiner for Baseline exam as for their post-baseline exam
- Subjects with the highest (top 50%) and Lowest (lowest 50%) Number of Bleeding Sites at Baseline
- By Age (< median age vs. ≥ median age)
- Subjects who completed all monthly visits
- By Gestational Age at enrollment (8 to ≤12 weeks, >12 to ≤16 weeks, >16 to ≤20 weeks, >20 to ≤24 weeks)

Oral Hygiene questionnaire data will be summarized by treatment group at Baseline and Month 3 visits.

Additional analyses may also be performed in order to more fully understand the data.

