Subjects will be asked to read and sign duplicate copies of the informed consent form which will be witnessed by site staff. Subjects will be given one signed copy of the informed consent form and the other signed copy will be maintained as site source documentation. Personal medical history information will be reviewed and retained as site source documentation; concomitant medications, height and weight will be recorded in the study database. Demographic information and entrance criteria will be assessed. Subjects will complete a survey on oral hygiene and prenatal knowledge and practices. A comprehensive oral examination will then be conducted to evaluate the oral and perioral region, including hard and soft tissues. Optionally, intraoral photographs may be taken. A trained and calibrated dentist will measure gingivitis and periodontal pocket depth. Gingival crevicular fluid samples and bacterial samples will be collected at two sites; sample collection sites will be recorded. Blood will be collected by venipuncture. Each sample will be stored for potential subsequent analysis. General comments and adverse events, if applicable, will be recorded.

Subjects will be randomly assigned to either the control group or the regimen group. The B&A computer program will assign a kit box number to a subject upon entry of the subject's stratification data. The subject number and kit box number will be recorded on forms provided by the Sponsor and/or suitable forms provided by the site. The kit box number assignment will be maintained and used for subsequent study product dispensing. Subjects will be given study products, instructed on product use and the first study product use will be supervised. All subjects will receive customary oral hygiene instruction, and in addition, subjects assigned to the regimen will receive counseling on oral hygiene, including an educational DVD on oral hygiene for personal use. All clinical examinations and interviews will be conducted by study personnel that are blind to treatment assignment, and uninvolved with oral hygiene education or product use training. The examiner will be in an area separate from randomization, product distribution, oral hygiene instruction and supervised use.

## Month 1 Visit 2

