## 10. Method of Assigning Subjects to Treatment Groups

Study Design	Total n	n/site	n/group/site	Strata	Cut-offs	
Parallel	750	300-450	150-300	History pre-term birth Current smoker Number of bleeding sites	Yes/No Yes/No (< 60 , ≥60)	

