#### B&A Computer Program

A separate randomization will be generated for each of the study sites with approximately equal numbers of subjects randomized at each site (300-450) and approximately equal numbers of subjects assigned to each of the treatment groups (150-300) at each study site to meet the overall recruitment target of 750 subjects. Eligible subjects will be randomly assigned equally to one of the two treatment groups. Each randomization will balance for history of pre-term birth, smoking and number of bleeding sites. Within strata, subjects will be randomly assigned to one of the treatment groups using an encoded program or randomization schedule supplied by the Sponsor.

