## 18. Statistical and Analytical Plans

Statistical analyses for gingivitis efficacy will be based on whole-mouth average Löe-Silness change from baseline scores (Baseline score minus post treatment score) and will be considered the primary variable. An analysis of covariance (ANCOVA) will be performed to determine treatment differences on the whole mouth average gingivitis reduction scores with the baseline gingivitis score as the covariate and also including study site as a factor. The interaction between treatment and study site will also be assessed. Additionally, 95% confidence intervals will be generated on the treatment difference for the average change from baseline scores. Separate analyses will be performed for each visit. The within-treatment difference from baseline gingivitis score will also be tested versus zero at each visit using the same ANCOVA model.

Statistical analyses to determine treatment differences for mean gestational age or other maternity endpoints will be analyzed using an analysis of variance (ANOVA) model with demographic factors such as (but not limited to) evidence of pre-term birth and smoking, and also using study site as a factor. Confidence intervals will be generated on the treatment difference of the mean gestational age.

If any of the data does not satisfy the normality criterion, analogous nonparametric methods will be employed. Additional analyses may also be performed in order to more fully understand the data. All treatment comparisons will be considered two-sided with an  $\alpha$ =0.05 significance level. In addition, gestational age will be categorized as preterm (gestational age < 37 weeks) or term (gestational age  $\geq$  37 weeks) for subsequent analyses. Other categories may be used to identify very early term births. Additional subgroups may be analyzed for birth outcome data, such as subjects with deliveries greater than or equal to 20 weeks of gestational age.

Demographic and baseline variables will be summarized by treatment group, and adverse events reported or noted during the study will be documented, listed and coded by treatment group.

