2. STUDY OBJECTIVES AND DESIGN

This is a multicenter randomized, controlled, single-blind, 2-treatment, parallel group clinical trial to assess gingivitis and maternity outcomes in pregnant women who undertake an advanced daily oral hygiene program. Up to 750 subjects were to be enrolled to complete the study with a target population of approximately 600 evaluable subjects. Subjects were adult female volunteers with moderate-to-severe gingivitis who were in their late first trimester or early-to-mid second trimester of pregnancy (8-24 weeks of pregnancy).

Sufficient screening was conducted to enroll approximately 300 evaluable subjects at each of two study centers. After informed consent was obtained, the baseline measures were recorded and subjects were randomized to either: 1) an advanced oral hygiene regimen consisting of marketed rechargeable toothbrush, toothpaste, mouth rinse and floss plus oral hygiene education counseling (Regimen), or 2) regular oral hygiene with an anticavity toothpaste, regular manual toothbrush and floss (Control).

Separate randomizations were generated for each study site with approximately equal numbers of subjects randomized to both groups. Each randomization was balanced for history of pre-term birth, smoking status and number of bleeding sites.

Study-related evaluations were scheduled, where possible, as part of routine prenatal visits. Dental examinations were conducted at Baseline before study product assignment, and monthly thereafter for 3 consecutive months of study product use. Product distribution took place at the monthly visits or via shipment when the subjects were not present for the monthly evaluation. Adverse events were collected from examination and interview. Oral hygiene and prenatal knowledge and practices were assessed by survey at Baseline and Month 3 visit.

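### The primary Löe-Silness model omits the three factors balanced within site at randomisation, and the SAP hypotheses cite a demographic adjustment that the model does not contain (minor)

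*SAP*

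**What the plan says.** **Randomisation.** The strata table in Protocol section 10 lists "History pre-term birth Current smoker Number of bleeding sites", the last cut at 60. The text below it says "Each randomization will balance for history of pre-term birth, smoking and number of bleeding sites", with a separate randomisation for each site. SAP section 2 reports the same three factors in the past tense: "Each randomization was balanced for history of pre-term birth, smoking status and number of bleeding sites". At the Baseline visit (Protocol section 3) the assignment program "will assign a kit box number to a subject upon entry of the subject's stratification data".

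**Primary model.** Protocol section 18 specifies an ANCOVA on the Löe-Silness change "with the baseline gingivitis score as the covariate and also including study site as a factor", with the treatment-by-site interaction also assessed. SAP 6.3 keeps the same main terms: "with the baseline gingivitis score as the covariate and also including study site, treatment, and the interaction of site and treatment". It adds a check of treatment by baseline score and drops interactions that are not significant at the 10% level. SAP 6.0 makes the Month 3 comparison the primary test.

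**Hypotheses.** The Protocol section 17 primary hypothesis concerns the "change from baseline score at each visit when an adjustment is made for the baseline Löe-Silness score" and names no other adjustment. Both SAP 6.3 hypotheses adjust for the "respective baseline gingivitis score and other demographic parameters".

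**Birth outcomes.** By contrast, the SAP 6.4 model does include prior preterm birth and smoking.

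**The concern.** There are two separate issues.

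1. **Analysis and design differ.** Balancing on a factor that predicts the outcome lowers the true variance of the treatment difference. The ordinary ANCOVA standard error shows that reduction only if the factor is in the model. If it is left out, the reported standard error is too large, the confidence interval too wide and the test conservative. If the factor does not predict the outcome, nothing is lost. Site and baseline score are already in the model. Baseline score also carries much of the bleeding-site information, because bleeding is derived from the same site scores (SAP 5.2). The gap is therefore mainly smoking and prior preterm birth.

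2. **The SAP hypothesis and the SAP model name different adjustments.** The model list is definite and contains no demographic term, so the hypothesis wording is the anomaly. Left as it is, a reader could argue later that some demographic covariate was pre-specified, or that a required adjustment was not made.

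**Working it through.** **Inputs.** 300 per group, difference 0.05, variability 0.185 and power of at least 90% (Protocol section 11, SAP 6.8); two-sided 5% level (SAP 6.0). I read 0.185 as the SD left after baseline score and site; the documents do not say which SD it is. They also give no R² for the balancing factors, so R² below is an assumption: the share of that remaining variance explained by the three factors.

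**The plan's own figure.**
- SE = 0.185 × √(2/300) = 0.01511
- Power = Φ(0.05/0.01511 − 1.96) = 0.9115

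The stated power of at least 90% is met.

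**With and without the factors.** Under balanced allocation the true SE is SE × √(1 − R²) for both models. The adjusted model reports that value; the current model still reports 0.01511.

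- Current power = Φ((0.05 − 1.96·SE) / (SE·√(1 − R²)))
- Adjusted power = Φ(0.05 / (SE·√(1 − R²)) − 1.96)
- Current type I error = 2Φ(−1.96/√(1 − R²))
- 95% CI half-width = 1.96 × reported SE

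| Assumed R² | True SE | Power, current | Power, adjusted | Gain (points) | Type I error, current | Half-width, current | Half-width, adjusted |
|---|---|---|---|---|---|---|---|
| 0% | 0.01511 | 91.15% | 91.15% | 0 | 0.0500 | 0.0296 | 0.0296 |
| 1% | 0.01503 | 91.26% | 91.42% | 0.16 | 0.0489 | 0.0296 | 0.0295 |
| 5% | 0.01472 | 91.70% | 92.45% | 0.75 | 0.0443 | 0.0296 | 0.0289 |
| 10% | 0.01433 | 92.27% | 93.69% | 1.42 | 0.0388 | 0.0296 | 0.0281 |

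The gain is measured against a current model that already benefits from balanced allocation. Measured against a fixed 91.15% it would look larger (93.69 − 91.15 = 2.5 points at R² = 10%), which overstates it.

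**Simulation check.** 15,000 trials per R² value, 600 women, permuted blocks of 4 within the 16 site-by-factor cells. Assumed: 15% prior preterm birth, 20% smokers, correlation 0.9 between baseline score and the score behind the bleeding category, and the extra R² split equally between prior preterm birth and smoking. For R² = 0, 1, 5 and 10%:

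- Type I error, current model: 0.0479, 0.0514, 0.0425, 0.0397
- Type I error, adjusted model: 0.0484, 0.0519, 0.0481, 0.0512
- Power, current model: 0.9099, 0.9094, 0.9163, 0.9217
- Power, adjusted model: 0.9103, 0.9115, 0.9245, 0.9364

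The Monte Carlo error on the type I figures is about 0.002, so the conservatism is visible at 5% and 10% but not at 1%.

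**Cost in degrees of freedom.** With the interactions dropped, 600 women and four parameters leave 596. Three more terms leave 593. The critical t moves from 1.96395 to 1.96397.

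**The case against.** **The efficiency gain may be nil.** No passage links smoking or prior preterm birth to gingivitis change; the documents name them as adjustment factors only for birth outcomes. At R² of 0 to 1% the half-width moves by at most 0.0001 on a 0 to 3 index. The model also has the protocol's own main terms and fits the protocol hypothesis. On this view the covariates are a preference and the only real defect is one phrase in SAP 6.3. This largely stands, and it is why the point is minor. It does not argue against a change that costs almost nothing.

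**The formulas are idealised.** They assume exact balance in the analysed set, while the primary population is the evaluable one, after exclusions for missed visits, product supply and one examiner's baseline readings. The block size is also assumed, since the documents give none. This is true but not decisive: in a simulation with 20% lost at random, the current model's type I error at R² = 10% was 0.043, still conservative, and adjustment removed the shortfall.

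**The randomisation values may not be in the study database.** The protocol says that they were entered into the assignment program, not where they were kept. The stratum is current smoking, whereas SAP 5.1 collects smoking during pregnancy. This stands as a practical matter to settle.

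**Changing the model creates a new mismatch with Protocol section 17**, which adjusts for baseline score only. This is correct, and the fix has to cover it.

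**Conclusion.** The concern holds and is minor. The omission and the mismatch within SAP 6.3 can both be read directly from the text. The primary test is unbiased, does not inflate type I error and meets its stated power without any change. The only statistical cost is a reported standard error that is slightly too large if the factors are prognostic: 0 to 1.4 points of power, and an actual type I error of 0.050 down to 0.039, over an assumed extra R² of 0 to 10%. Those sizes rest on reading 0.185 as the residual SD and on near-exact balance in the analysed set. The low end of the range is the safer reading. The wording conflict depends on none of these assumptions and needs correcting in any case.

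**What to change.** Before the blind is broken:

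1. In SAP 6.3, add prior preterm birth, smoking and the bleeding-site category (below 60, 60 or more) as main effects in the Löe-Silness ANCOVA, using the values entered at randomisation. If those cannot be retrieved, name the collected baseline variables that replace them.
2. Do the same for pocket depth. In the bleeding-site model add only prior preterm birth and smoking, because the baseline count itself is already the covariate there.
3. Reword the SAP 6.3 hypotheses so that they list exactly the terms in the model.
4. Record the change in SAP section 3 as a departure from the Protocol section 18 model and the section 17 hypothesis. The sponsor should decide whether the amendment rule in Protocol Appendix 1 applies.

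If the protocol model is kept instead, delete the reference to demographic adjustment from both SAP 6.3 hypotheses. That alone restores consistency.

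The cost is low: text edits, one entry in SAP section 3, a decision on an amendment, retrieval of the stratification values, and 3 of about 596 degrees of freedom. No new data collection is needed. SAP 5.5 has the plan completed before unblinding, so the model can still be settled then.
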